before at T = 0 and serial MRS scans and blood samples will be collected at T = 5 and 14 hours. On Day 36, following an overnight fast, a final MRS scan will be performed alongside a blood test at T = 24 hours.

A follow-up visit will be performed 28 days after the last dose of investigational product for safety assessments.

TARGET SUBJECT POPULATION

Subjects aged \geq 18 years, with body mass index \geq 27 and \leq 40 kg/m², a diagnosis of T2DM on metformin monotherapy, and a glycated haemoglobin of \leq 8.0% will be enrolled in the study. Females must not be pregnant and lactating females will be excluded. Females of childbearing potential should be using appropriate contraception.

TREATMENT GROUPS AND REGIMENS

Part A:

Following a screening period of up to 60 days, subjects will be randomised to receive either MEDI0382 or placebo once daily in the morning via SC injection as follows:

- MEDI0382 [REDACTED]
- Placebo for 28 days (N = 10)

Part B:

Following a screening period of up to 60 days, subjects will be randomised to receive either MEDI0382, placebo, or open-label liraglutide once daily in the morning via SC injection as follows:

- MEDI0382 [REDACTED]
- [REDACTED]
- Open label liraglutide 0.6 mg for 7 days, followed by 1.2 mg for 7 days, followed by 1.8 mg for 21 days (N = 10)

STATISTICAL METHODS

Sample size:

In Part A the sample size of 8 completers in each MEDI0382 and placebo groups provides \sim 80% power to detect a difference of 19% reduction in the baseline glycogen concentration adjusted for liver volume (as measured by MRS at T = 4 hours post standardised liquid morning meal) after 28 days of treatment in the MEDI0382 versus placebo arms. This is under the assumption of baseline glycogen content of 283 μ mol/mL and standard deviation of 41 μ mol/mL for both groups and a two-sided significance level at 0.1 (Krssak et al, 2004; Rothman et al, 1991).

In Part B the sample size of 10 completers in each MEDI0382 and placebo groups provides $>$ 80% power to detect a 24.2% reduction in fasting glycogen concentration adjusted for liver volume (as measured by MRS at T = 24 hours post standardised liquid morning meal) after 35 days of treatment in the MEDI0382 versus placebo arms. This is under the assumption of a common standard deviation of 17.0 % for both groups, a two-sided significance level at 0.05 and is based on the results of Part A.

Statistical analyses:

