3.2.2 Rationale for Study Population

3.2.3.1 Primary Endpoint

The primary endpoint of change in hepatic glycogen adjusted for liver volume 4 hours (Part A) after a standardised meal has been chosen as this corresponds to the time at which the greatest effect of MEDI0382 on glycogen levels would be predicted to occur. Studies in subjects evaluating hepatic glycogen stores (in some cases using a C-13 labelled glucose) have shown that peak glycogen levels are observed at 4 to 5 hours post-ingestion of a meal (Krissak et al, 2004, Moore et al, 2017, Magnusson et al, 1992), and this timing coincides with the time of maximal plasma concentration of MEDI0382 at approximately 4 hours.

The primary endpoint of % change in fasting glycogen adjusted for liver volume has been selected for Part B as a statistically significant reduction in fasting glycogen (at both T = 0 and T = 24 hours) was observed in Part A and variability at these time-points was lower than other time-points permitting a smaller sample size. The T = 24 hour fasting time-point has been selected rather than the T = 0 hour time point to perform the analysis as this is optimal from an operational perspective.

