4.8 Statistical Evaluation

4.8.1 General Considerations

Tabular summaries will be presented by treatment group. Categorical data will be summarised by the number and percentage of subjects in each category. Continuous variables will be summarised by descriptive statistics. The study objectives will be evaluated on Part A and Part B separately and also on the combined cohorts as appropriate. Additional details of statistical analyses will be described in the statistical analysis plan.

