2.2 Study Design

This exploratory Phase 2 study has 2 parts (Part A and Part B).

Part A is a randomized, double-blind, placebo-controlled sub-study to evaluate the effect of MEDI0382 ([REDACTED] administered once daily SC for 28 days on hepatic glycogen metabolism in overweight or obese subjects with T2DM. Part A is planned to randomize up to 20 subjects. Subjects will be consented, screened for suitability, and randomized within 60 days if eligible. Subjects from Part A will not be re-enrolled in Part B.

Part B is contingent on the results from Part A such that the combined sample size of two parts will ensure at least 80% power to detect the treatment effect observed from Part A using the standard deviation information also observed from Part A. If the minimal required sample size for Part B is less than or equal to 10 subjects per arm, Part B will be conducted.

Part B is an exploratory Phase 2 randomized, double-blind, placebo-controlled and open label active comparator sub-study to evaluate the effect of MEDI0382 on hepatic glycogen metabolism in overweight and obese subjects with T2DM subjects with the exact sample size determined by the results from Part A. Subjects in Part B will be randomized to receive double-blind MEDI0382 ([REDACTED]) or placebo or open label liraglutide (titrated from 0.6 to 1.8 mg) once daily SC for 35 days.

Part A:

The study will involve measurement of hepatic glycogen content using a carbon (C)-13 MRS based technique before and after 28 days of treatment. Subjects will undergo a 5-day washout

period where metformin therapy will be suspended at the beginning of the study starting from Day -4 (metformin dosing to resume on Day 2) and the end of the study starting from Day 25 (metformin dosing to resume on Day 30). Across the course of the study (up to 126 days in total including screening) subjects will have a total of 6 study visits, 6 nights of inpatient stay and will undergo a total of 10 MRS scans alongside additional assessments and blood sampling.

Part B:

In Part B a comparison will be made between MEDI0382, [REDACTED] [REDACTED] placebo and liraglutide once daily titrated from 0.6 to 1.8 mg in 7-day intervals. The treatment duration will be 35 days in each treatment group, with subjects randomized to liraglutide spending 21 days at 1.8 mg, in contrast subjects randomized to MEDI0382 will spend 14 days at top dose of 300 µg.

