3 STATISTICAL METHODS

3.1 General Considerations

In the event that there is a delay in data delivery or the full set of results is not expected to be available in timely manner (for example; follow-up of positive ADA results at 3 and 6

months after the follow-up visit) an initial database lock in Part B for the purpose of clinical study analysis and reporting will be performed when the last randomized subject completes the final visit or is discontinued prior to that visit. Final database lock will occur once all results have been received in the database.

In the event that an initial DBL is required, results received after this point may be reported in the clinical study report addendum.

Data will be presented in data listings sorted by study part, treatment, subject number and date collected, where appropriate. Tabular summaries will be presented by study part and treatment. Categorical data will be summarized by study part and treatment with the number and percentage of subjects within each category. In general, continuous variables will be summarized by study part and treatment with descriptive statistics including mean, standard deviation, median, minimum, and maximum. For some variables, the geometric mean and 95% CI may be presented.

All available data will be included in the analyses and missing data will not be imputed except as specified in the calculation of the AUC values. Unless specified otherwise, baseline values will be defined as the last valid assessment prior to the first administration of study medication.

The study objectives will be evaluated with analyses that include data from both Part A and Part B, if Part B is conducted. Analyses will also be performed separately for each study part. In general, the efficacy analyses will be analyzed with the ITT population and all other analyses will be performed with the As-treated population.

All statistical tests will be 2-sided at an alpha = 0.1 significance level unless stated otherwise. There will be no adjustment for multiplicity.

Data analyses will be performed using SAS[®] version 9.3 or higher (SAS Institute Inc., Cary, NC) in a UNIX environment.

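### SAP 3.1 provides for pooled Part A + Part B evaluation that SAP 3.4 does not reconcile; for fasting glycogen, pooling would re-use the Part A data that led to the choice of endpoint

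*SAP*

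**What the plan says.** **Pooling.** SAP 3.1: "The study objectives will be evaluated with analyses that include data from both Part A and Part B, if Part B is conducted". Separate analyses by part are to be done as well. Protocol 4.8.1 is softer; it evaluates the parts separately and "also on the combined cohorts as appropriate". The SAP drops that qualifier.

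**Error control.** SAP 3.1: "All statistical tests will be 2-sided at an alpha = 0.1 significance level unless stated otherwise", and "There will be no adjustment for multiplicity".

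**Choice of endpoint.** Protocol 3.2.3.1 explains that fasting glycogen became the Part B primary endpoint because "a statistically significant reduction in fasting glycogen (at both T = 0 and T = 24 hours) was observed in Part A", and because variability was lower at those time points.

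**Link between the parts.** SAP 2.2 makes Part B contingent on Part A and frames power on the combined sample: "If the minimal required sample size for Part B is less than or equal to 10 subjects per arm, Part B will be conducted". The Protocol Synopsis (Sample size) assumes a 24.2% reduction and SD 17.0% for Part B, with "a two-sided significance level at 0.05 and is based on the results of Part A".

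**Named tests.** SAP 3.4.1.3 labels the T = 24 h primary ANCOVA as Part B only. SAP 3.4.2.2 gives one T = 24 h ANCOVA against placebo in Part A and one against liraglutide in Part B. No combined fasting-glycogen model is written.

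**The concern.** Two parts of the SAP point different ways. A programmer following 3.1 would pool the parts for the placebo comparison; one following 3.4 would not. Percentage change at T = 24 h is defined in both parts, so pooling is feasible. The model, the weighting and the inferential status of the result are left open, although Part A has already been analysed (SAP 4).

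For this endpoint the choice matters. With 8 to 10 Part A subjects per arm and 10 in Part B, 44% to 50% of the pooled data (8/18 to 10/20) would be the data that suggested the hypothesis. An ordinary pooled test treats them as if the endpoint had been fixed beforehand. It could then appear to confirm the fasting effect largely on Part A, even if the independent Part B showed little.

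**Working it through.** **Inputs**
- Effect 24.2 and SD 17.0 (percentage points): Protocol Synopsis, Sample size. Taking them as the Part A observed values is an assumption, supported by the statement that the sizing rests on Part A.
- Part A: 8 completers per arm planned (Protocol 3.1.2), with 10 per arm randomised as an upper bound (Synopsis). The actual number is not given.
- Part B: 10 completers per arm (Synopsis).
- Alpha: 0.10 (SAP 3.1) and 0.05 (Part B sizing).

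**Step 1. Reproduce the plan's power.** For Part B the noncentrality is 24.2 / (17 × √(2/10)) = 24.2 / 7.60 = 3.18. With 18 df and two-sided 0.05, power is 0.853 (normal approximation 0.889), in line with the stated >80%. For Part A, 19% of 283 is 53.8; with SD 41, 8 per arm and alpha 0.10, power is 0.802 against the stated ~80%.

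**Step 2. Pooled test with Part A fixed and no true effect in Part B (closed form).** Let N = nA + nB per arm.
- Mean pooled difference = nA × 24.2 / N.
- Critical difference = t × 17 × √(2/N), with 2N − 2 df.
- SD contributed by Part B = (nB/N) × 17 × √(2/nB).
- P(significant) = 1 − Φ((critical − mean) / SD).

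| nA + nB | Mean | SD from Part B | Critical 0.10 / 0.05 | P at 0.10 / 0.05 |
|---|---|---|---|---|
| 8 + 10 | 10.76 | 4.22 | 9.58 / 11.52 | 0.609 / 0.429 |
| 9 + 10 | 11.46 | 4.00 | 9.31 / 11.19 | 0.705 / 0.528 |
| 10 + 10 | 12.10 | 3.80 | 9.06 / 10.88 | 0.788 / 0.626 |

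For 8 + 10 at 0.10: (9.58 − 10.76) / 4.22 = −0.28, giving 0.61.

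**Step 3. Re-estimate the residual variance (simulation).** The closed form holds the SD at 17. In a plain pooled t-test the disagreement between the parts enters the residual and lowers the rates. This simulation assumes the same mean placebo change in both parts.

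| nA | Pooled t-test, 0.10 / 0.05 | With a part term, 0.10 / 0.05 |
|---|---|---|
| 8 | 52% / 34% | 56% / 39% |
| 9 | 60% / 42% | 65% / 47% |
| 10 | 69% / 51% | 73% / 56% |

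A part term does not help, because the Part A difference stays in the estimate.

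**Step 4. Smaller Part A effect.** With 20 instead of 24.2, the pooled t-test gives about 39% to 53% at 0.10 and 24% to 35% at 0.05.

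**Step 5. No effect in either part.** Given a significant favourable Part A result (at 0.05 or 0.10), a favourable pooled test at 0.10 follows in about 35% to 48% of trials. The joint chance of both is only about 1% to 2% for one time point. If the best of Part A's five scan times is picked, it is about 4% to 7% (assumed correlation 0.5 between times). The nominal favourable tail is 5%.

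**The case against.** The strongest reply is that the plan specifies no pooled fasting-glycogen test. The named tests are each tied to one part, the protocol pools only where appropriate, and a pooled endpoint would have to mix 28 and 35 days of treatment. That stands, so the defect is an unreconciled general statement and not a flawed named analysis. But SAP 3.1 says the objectives will be evaluated on both parts, SAP 2.2 frames power on the combined sample, and 3.4 does not withdraw either. For the exploratory pharmacodynamic endpoints, SAP 3.5.1.2 does restrict analysis to the separate parts, so the SAP rules out pooling where it means to.

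Second, the 52% to 69% is conditional on Part A. A reader might infer an overall false-positive rate of about half. The documents do not support that. If Part A reflects a real effect, a significant pooled result is not an error, and the joint rates in Step 5 are far lower. They exceed 5% only if several time points were searched. The conditional rate is still the relevant one for reading a pooled p-value now, because Part A is known and the endpoint has been chosen from it.

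Third, a reader might infer that a favourable fasting result opened Part B. SAP 2.2 does not name the endpoint behind that rule, and the Part A primary was T = 4 h. Only the choice of endpoint is documented as following from the fasting result.

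Fourth, the study is exploratory and openly makes no multiplicity adjustment. That lowers the stakes, though Part B still has a primary hypothesis sized at 0.05.

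**Conclusion.** The concern holds in limited form. SAP 3.1 and 3.4 are not reconciled, and if 3.1 is applied to fasting glycogen versus placebo, the p-value and estimate are biased towards an effect by selection on Part A.

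With zero true effect in Part B, the plain pooled test would be significant in about 52% to 69% of trials at 0.10 and 34% to 51% at 0.05, with a mean pooled reduction of about 11 to 12 points. These figures rest on 24.2 and 17.0 being the Part A results and on 8 to 10 per arm in Part A. The ANCOVA baseline adjustment is not modelled, because no baseline correlation is given. The detailed sample-size sections are redacted, so the synopsis was used.

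It would be wrong to conclude that the Part B primary result is compromised. That test uses Part B data only and, with no effect, keeps its nominal level (5% or 10%, according to the alpha applied).

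**What to change.** Add to SAP 3.1:

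> For fasting glycogen, MEDI0382 versus placebo, the confirmatory test is the Part B-only ANCOVA in SAP 3.4.1.3. The Part A ANCOVA in SAP 3.4.2.2 is kept and reported separately as hypothesis-generating. Any combined Part A + Part B result for fasting glycogen is descriptive, without a p-value, and footnoted that it includes the Part A data used to select the endpoint.

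This keeps the prespecified Part A secondary test, which a blanket rule limiting all fasting-glycogen tests to Part B would delete. Combined analyses of endpoints not selected on Part A results can stay.

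The cost is SAP wording and the loss of a pooled p-value for fasting glycogen. No subjects, visits or procedures change.

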3.2 Analysis Populations

The analysis populations are defined in [Table 3.2-1](#).

Table 3.2-1 Analysis Populations

Population	Description
Intent-to-treat (ITT) population	Subjects who receive any study investigational product will be included in the ITT population and subjects will be analyzed according to their randomized treatment group.
As-treated population	Subjects who receive any study investigational product will be included in the as-treated population and subjects will be analyzed according to the treatment they actually received.
Pharmacokinetic population	The PK population includes all subjects who received at least one dose of investigational product and had at least one PK blood sample taken that is above the lower limit of quantitation.

3.3 Study Subjects

3.3.1 Subject Disposition and Completion Status

A summary of subject eligibility and randomization as well as treatment group received (including summary of subjects randomized but not treated) will be provided by study part. In addition, disposition of subjects throughout the study with respect to completion of treatment and follow-up will be provided.

3.3.2 Demographics and Baseline Characteristics

Demographic information and baseline characteristics will be summarized by study part and by treatment. Demographic information will include: gender, age (years), ethnicity, race, weight (kg), height (cm), and body mass index (BMI) (kg/m²). A summary of baseline characteristics may include but not limited to eGFR, baseline medication use, HbA1c, glucose, blood pressure, and pulse rate.

3.3.3 Study Drug Exposure

The number of doses and total dose received will be summarized by study part for each investigational product (MEDI0382 or placebo or liraglutide) by descriptive statistics and frequencies.

3.3.4 Concomitant Medications

Concomitant medications will be coded using the current WHO Drug Dictionary enhanced (WHO-DD). The number and percentage of subjects who took concomitant medications for the highest anatomical therapeutic chemical (ATC) class and preferred term will be summarized by study part and treatment. The summary of concomitant medications will include all concomitant medications taken on or after the date of first dose of investigational

product or any concomitant medication started prior to first dose of investigational product that continued beyond the date of first dose of investigational product.

3.4 Efficacy Analyses

3.4.1 Primary Efficacy Endpoint(s) and Analyses

3.4.1.1 Primary Efficacy Endpoint(s)

Change in hepatic glycogen concentration adjusted for liver volume as measured by MRS at T = 4 hours post standardized morning meal from baseline (Day -1) to the end of 28 days of treatment (Part A only)

Percentage change in fasting glycogen concentration adjusted for liver volume as measured by MRS at T = 24 hours post standardized morning meal from baseline (Day 1) to the end of 35 days of treatment (Part B only)

3.4.1.2 Handling of Dropouts and Missing Data

Since there is only one post-baseline measurement MRS, subjects who do not have a valid baseline evaluation or a valid Day 28 (Part A) and Day 35 (Part B) MRS evaluation at 4 hours (Part A) and 24 hours (Part B) post standardized morning meal will not contribute to the analysis.

